3.4 Summary of progress and preliminary results

With start-up funds obtained from CIHR and other sources, we launched the prospective cohort at 13 centres and have recruited 77 patients from 6 centres to date. The remaining 7 centres are either approved or close to full approval (ethics and contracts). All sites will be recruiting by June 2015 – demonstrating feasibility to complete the work plan as described in this proposal. Our preliminary data is provided in the Appendix. Baseline demographics of the patient and physician cohort enrolled to date are shown in

Tables 7 & 8. Preliminary data from the cohort demonstrating variation in steroid prescriptions by key patient demographic variables and by type of episode of treatment are shown in Tables 9a-c. Graphical representations of steroid prescribed per episode for different patient scenarios are shown in Figures 7a-d. Variation in steroid prescriptions between physicians within one site and variation in steroid prescriptions between sites are shown in Tables 10 and 11 respectively. We also show differences among patients in ‘time on and off steroids’ by site in Figure 8, and the average daily steroid dose over time by site in Figure 9. Finally, in Figure 10 and Table 12, we show differences in relapses (survival curve, and absolute relapse numbers) by site.

4.0 LIMITATIONS AND CONTINGENCY PLANS

There are several limitations of our work that must be acknowledged. Recruitment into the cohort study may be slow at times due to either seasonal variation in incidence of disease, or due to unforeseen site based challenges in recruitment. In the early phases of this study, we have demonstrated increasing recruitment rates. We will sustain recruitment by providing monthly enrolment reports, study reminders and scientific updates to site investigators. We will hold annual face-to-face investigator meetings to monitor study progress, build cohesion amongst members and solve any issues that may arise during the study. We may miss enrolment of patients living in non-metropolitan regions, particularly those who are managed by general pediatricians; however, we estimated this loss to be <5%. Contamination of treatment protocols may occur due to the study itself and resulting increased interactions between physicians within sites and between sites. We acknowledge that due to the national scope of this study, and its aims, we may influence practice over time; this is unavoidable and indicates the impact and novelty of the study. Furthermore as new evidence emerges such as the recent RCTs, practice may be influenced. To address changing practice over time we will monitor for and report this trend within the data. We may not capture all unknown confounders at centre, physician and patient levels despite our detailed data collection. For example, tracking patient adherence to steroid therapy would reduce some confounding due to non-adherence; such monitoring is beyond the scope of this study but will be part of our future work.

We also carefully considered potential areas where the analytic plan may fail to answer our research questions. We considered whether we will observe variation in care at all three levels in a relatively small patient sample and particularly small and potentially homogeneous physician groups. We are reassured by examining our preliminary data that even with fewer than a hundred patients, we are able to detect variation between sites, between physicians within centres, and within physician between patients. If we were to see homogeneity among physician groups within centres (e.g. cohesive physician groups with centre specific standardized protocols), we will reduce our model to two levels – centre and patient, if needed.

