2.6 There is uncertainty in the literature regarding best treatment protocols for childhood nephrotic syndrome. The evidence supporting many guideline recommendations for steroid therapy and second line agents are based on small numbers of randomized controlled trials (RCTs), some with very few patients – leading to lack of trust among the physician groups in the robustness of the literature.^{44,45} In addition, the literature continues to evolve with conflicting messages. Three recent RCTs (2 in the same January 2015 *Kidney International* issue) were published; they all suggest that there is no benefit to prolonged steroid treatment of up to 6 months compared to 3 months for first presentation of nephrotic syndrome.⁴⁶⁻⁴⁸ A recent editorial published with these new RCTs suggest that future trials should no longer just focus on duration of steroid therapy over the short term, but rather study emerging novel treatments for nephrotic syndrome and long term outcomes.⁴⁵ In the light of new evidence, and prevalent practice variation, we believe that a national observational cohort study is *a necessary first step* to obtain valuable generalizable data. These data will: 1) inform whether there is a need to develop standardized protocols to reduce practice variation by identifying differences in patient outcomes based on steroid prescribed; 2) provide observational patient outcome data to complement interpretation of published short term clinical trial results; and 3) assist in strategic prioritization of future clinical trial questions regarding new and old therapeutics.

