Outcome: The primary outcome of interest is relapse rate (number of relapses/per person unit time). Relapse rate is the most clinically relevant outcome for nephrotic syndrome and the best indicator of morbidity experienced by patients; this outcome definition is consistent with prior literature in this area.⁴⁰

Exposure: The exposure is steroid prescribed per unit time - that is the total dose patients were prescribed as treatment for episodes of proteinuria divided by the sum of duration of 'days on steroids' during observation period. Days on steroids is defined by the sum of the length in days of all episodes (see definition of episode in section 3.1, also graphically represented in Appendix Figure 4) observed. This definition is consistent with measures of steroid exposure used in prior nephrotic syndrome steroid dosing studies conducted in Europe and in a Canadian study of steroid associated osteoporosis in children.^{38,55} Systemic steroid exposure (both oral and intravenous) will be converted into prednisone equivalents (mg/m^2) using standard dose conversion tables and weight based dosing criteria [mg/kg] will be converted to mg/m^2 .

Analysis plan: The unit of analysis is the patient. Given that the main outcome of interest is relapse rate, we will use Poisson regression models with steroid prescribed per unit time as the exposure and relapse rate per unit time as the outcome, adjusting for patient level variables (age, gender, ethnicity, household income, parental education) and episode at entry into study (either first presentation, first relapse or second relapse), and taking into account time at risk. We are not using multi-level (hierarchical) analysis in this objective, as there is no clustering at the patient-level. There is only one measurement per patient, relapse rate adding all episodes experienced by one patient as a count.

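### The protocol foresees prescribing drift but answers it only with a trend report; neither objective's model contains calendar time, so drift may bias the estimates

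*Protocol*

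**What the plan says.** Section 4.0 names two sources of change in practice. On the study itself it says "we may influence practice over time; this is unavoidable and indicates the impact and novelty of the study". On outside evidence it says "Furthermore as new evidence emerges such as the recent RCTs, practice may be influenced". Section 2.6 describes that evidence: three recent trials suggesting that "there is no benefit to prolonged steroid treatment of up to 6 months compared to 3 months". The response in section 4.0 is "To address changing practice over time we will monitor for and report this trend within the data".

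Section 3.2 gives the Objective 1 model as a Poisson regression of relapse rate on steroid prescribed per unit time, "adjusting for patient level variables (age, gender, ethnicity, household income, parental education) and episode at entry into study", "and taking into account time at risk". The exposure is total dose over all observed episodes divided by total days on steroids.

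In section 3.3 (Objective 2) dose per episode is the outcome. The explanatory variables are one at centre level, three at physician level and four at patient level. The power paragraph counts the same total of 8. No calendar variable appears in either list.

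Section 3.1 sets 4.0 years of enrolment plus 6 months. Section 3.4 reports that the investigators "have recruited 77 patients from 6 centres to date", with all sites due to be recruiting by June 2015.

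**The concern.** Under a common study end, entry date largely fixes how long a child is followed. Late entrants are treated under the newest practice and contribute only the early part of their disease. Early entrants contribute early and later disease. If prescribing drifts and relapse frequency also changes with time since onset, entry date is related to both the exposure and the outcome of Objective 1. Neither the time-at-risk term nor episode at entry removes that link.

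In Objective 2 the threat differs. A time trend in the outcome (dose) may be attributed to centre or physician characteristics when centres or physicians contribute episodes from different calendar periods.

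Small biases matter because the effect the study says it can detect is small: an IRR of 0.989, presumably per 1 mg/m2 of average daily dose.

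**Working it through.** **1. The plan's own figure.** Inputs from section 3.2: N = 597, 2 years at risk, base rate 1.68 per person-year, dose SD 8.85, R² 0.2, two-sided alpha 0.05, power 90%.

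- SE of the log IRR = 1/√(597 × 2 × 1.68 × 8.85² × 0.8) = 0.0028.
- Detectable IRR = exp(−(1.960 + 1.282) × 0.00282) = 0.9909 if 1.68 is the rate at the mean dose.
- If 1.68 is the rate at dose zero, the same formula gives 0.9893, which rounds to the stated 0.989. The figure is reproduced on that reading.
- ln 0.989 = −0.0111 is the yardstick below.

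**2. When time at risk is sufficient.** With a constant relapse rate, the log-time offset gives an IRR of 1.000 whatever the dose drift. Follow-up length alone causes no bias.

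**3. When it is not.** Suppose the relapse rate falls at rate k per year since entry. The average over follow-up f is then proportional to (1 − e^(−kf))/(kf). Take f = 4.5 years for the first entrant and 0.5 for the last.

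- 15% per year (k = 0.1625): 0.709 against 0.961, ratio 1.35.
- 30% per year (k = 0.3567): 0.498 against 0.916, ratio 1.84.

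The last entrants therefore show a higher average rate even though dose does nothing. If dose has fallen by 1 to 3 mg/m2 per year, they also have doses 4 to 12 mg/m2 lower than the first entrants.

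**4. Size in Objective 1.** These are assumptions, not protocol figures: no true dose effect, n = 597, uniform entry over 4 years, common end at 4.5 years, mean rate 1.68, dose SD 8.85, Poisson model with offset, dose tied to entry date. The simulated rejection column gives the range over separate runs with slightly different set-ups. The last column uses the planned SE: shift = |ln IRR|/0.00282, rejection = Φ(shift − 1.96) + Φ(−shift − 1.96).

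| Dose fall per year | Relapse decline per year | Spurious IRR | Simulated rejection | Rejection at planned SE |
|---|---|---|---|---|
| 1 | 15% | 0.999 | 9–10% | 6–7% |
| 2 | 15% | 0.998 | 12–17% | 11% |
| 2 | 30% | 0.996 | 42–44% | 30% |
| 3 | 30% | 0.994 | 67–79% | 57% |

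The simulated SE is about 0.0023. It is below 0.0028 because mean follow-up is 2.5 years and no other covariates are correlated with dose. On the log scale the bias is 0.0010/0.0111 = 9% to 0.0060/0.0111 = 54% of the detectable effect.

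**5. Direction.** With dose rising by 2 mg/m2 per year and a 30% relapse decline, the spurious IRR is 1.004 and rejection is 41 to 47%.

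**6. Effect of adding entry date.** When dose is tied to entry date, adjustment returns the IRR to 1.000 and rejection to about 3 to 7%. The protocol's exposure is averaged over all episodes, however, so dose may follow episode dates. In one such simulation with a 30% decline, rejection fell from 43% to 11% (2 per year) and from 78% to 17% (3 per year). In another, where dose followed calendar time throughout follow-up, the unadjusted rates were lower, at 15% and 27%. Adjustment thus removes most of the bias, but not always all.

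**7. Objective 2.** The documents give no basis for a magnitude. The patients enrolled before all sites were open are 77 of 597, or 13%.

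**The case against.** The strongest counter-case has five parts.

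- **Follow-up length is already handled.** A reader might infer that Objective 1 ignores it. It does not: time at risk is in the model, and bias needs a trend in both dose and relapse rate. The protocol quantifies neither and says only that practice may change. This stands, and the point is conditional.
- **The sign is open.** A reader might infer that drift would manufacture the study's hypothesis of more steroid and fewer relapses. The documents do not support that. The cited trials concern course length, whereas the exposure is average dose per treated day. In section 2.3, going from 4 + 4 weeks to 6 + 6 weeks keeps the daily to alternate-day ratio, so at unchanged doses the daily average is the same. Losing a long low-dose tail would raise it. This stands.
- **Dose is not the exposure in Objective 2.** A reader might infer that both models confound dose with entry date. In Objective 2 dose is the outcome and the episode is the unit, so only centre and physician coefficients are at risk. The staggered start is limited, since all sites were due by June 2015. This stands.
- **The upper end is extreme.** A fall of 3 mg/m2 per year is 12 mg/m2 over enrolment, or 39% of the 30.64 mean and 1.4 SDs. This is fair, and the lower rows of drift give small inflation.
- **This could be left to an analysis plan.** It fails here. The protocol names the threat, states its answer, and enumerates the covariates of both models. The answer given describes the trend without adjusting for it.

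**Conclusion.** The point holds as a conditional risk. The protocol foresees drift, offers description as the remedy, and leaves calendar time out of both stated models. In Objective 1 the bias is zero if the relapse rate is constant. Otherwise it runs from negligible to material: an IRR of about 0.999 to 0.994 for assumed dose falls of 1 to 3 mg/m2 per year with relapse declines of 15 to 30% per year, and above 1 if dose rises. These trends are illustrative, as are uniform entry and a common study end. In Objective 2 a trend may mix into the centre and physician coefficients, to an extent the documents do not allow one to size. Nothing here shows that the estimates will be biased. The case for change is that the protocol raises the threat itself and the remedy is cheap.

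**What to change.** Add calendar date of entry (linear or in yearly categories) as a fixed effect in the Objective 1 model, and calendar date of episode start as a fixed effect in the Objective 2 models. Keep the descriptive trend report. State in the plan that entry-date adjustment removes most, not necessarily all, of the Objective 1 bias, because the exposure is averaged over all of a child's episodes.

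The cost is one covariate per model. Section 3.1 already records the start date of full-dose steroids for each episode. A ninth explanatory variable in Objective 2 still easily meets the 10-observations-per-variable guideline with at least 597 episodes. The loss of precision in Objective 1 is small. With dose tied to entry date, entry date explains d² × (16/12)/8.85² of the dose variance, where d is the yearly drift: 1.7% at 1 mg/m2 per year and 15% at 3. Inflating the SE by 1/√(1 − that share) adds about 1% and 9%. In simulation the SE went from 0.0023 to between 0.0023 and 0.0025.

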Supporting national infrastructure: We will receive mentorship and support from the Canadian Kidney Knowledge Translation and Generation Network (CANN-NET; www.cann-net.ca), a CIHR funded national network promoting best practices in nephrology. We will also receive support from the Maternal, Infant, Child, Youth Network (MICYRN). See attached letters from [name] and [name].

6.0 KT PLAN

Integrated KT plan: We are using an integrated KT model wherein decision-makers and end-users (pediatric nephrologists and parents) are engaged at all stages of the research process from priority setting and identification of key questions to interpretation and dissemination of results.^{65,66} The involvement of decision-makers and end-users throughout will be critical for the success of the research aims and to ensure efficient and timely data collection at all participating centres.

For all 13 Canadian pediatric nephrology centres, we have identified site investigators (see letters of support attached) who are acting as local champions for this Project. We also have strong support from the leadership of Canadian Association of Pediatric Nephrologists (see letter from [name], President). The Association has provided several opportunities for us to engage pediatric nephrologists at semi-annual meetings and will also assist with our KT plan.

We have recently engaged committed parents, from different geographical regions and backgrounds, who are willing to partner with the study team to ensure patients and families are engaged in KT and that patient and family priorities are addressed in the future directions of this national initiative (see support letter from [name], parent of child with steroid sensitive nephrotic syndrome). We will host at least 2 parent group teleconferences over the next 6 months to educate parents and/or patients about this national research initiative, our study plan and to learn from them about the daily challenges that they face, and how research might inform these. We envision that this will lead to a long-term meaningful engagement in KT and dissemination activities during this course of this study.

We are holding face-face to investigator and team meetings yearly in conjunction with the Canadian Society of Nephrology annual general meeting. We will also host a Canadian Childhood Nephrotic Syndrome Project Symposium on September 17 and 18 of this year in Calgary – to plan for the next steps and sequential building blocks in our research program. The symposium will bring together the national study team, both local and international experts, as well as basic and translational researchers

working in this area, in order to foster creativity and innovation through trans-disciplinary collaborations. The parent group will be invited to participate in this symposium and we will also use this opportunity to conduct a semi-structured group interview to elicit patient/parent priorities and ensure that these priorities align with our work plan for the future. We have applied for a CIHR planning and dissemination grant to fund this meeting.

In the final year of funding, all stakeholders (investigators, principal knowledge users, site investigators from all 13 sites, and invited experts including representation from parent/patient groups) will be invited to a face-to-face meeting to assist in the interpretation of study results. Both the quantitative and qualitative results of the study (description of cohort, clinical course including steroid exposure and use of second line agents by centre, physician and patient variables, association of variability in steroid treatment on relapse rates, results of multi-level mixed methods models showing factors significantly associated with variation in steroid treatment, and common themes regarding variation in care elicited from focus groups) will be presented. All clinical practice guideline recommendations will also be reviewed. Utilizing all this information, we will draft best practice approaches for treatment of first presentation and subsequent relapses of nephrotic syndrome acceptable to all stakeholders. We will develop an implementation plan, informed by results of Objective 2 (centre-, physician- and patient-level characteristics driving variability in care), and ensure that the comprehensive results of this study are disseminated to physicians and other relevant stakeholders within each centre.

End-of-grant KT plan: We published our study plan in the new journal of Canadian Journal of Kidney Health and Disease ([name] et al. 2014, see attached manuscript). Our next manuscript will describe the results of the qualitative study (target completion date June 2015). The remainder of our manuscript plan - to disseminate the quantitative and mixed methods results are detailed in the Appendix page 38, Gantt chart. We will present our findings at local (nephrology divisional rounds and pediatric grand rounds with telehealth connections to rural sites and primary care pediatrics offices), national (Canadian Society of Nephrology and Canadian Pediatric Society meetings) and international (American Society of Nephrology meeting, special interest group meetings for pediatric nephrology). The Principal Applicant, co-applicants and site liaisons are members of these organizations and will ensure effective and prompt dissemination of research findings to relevant knowledge user groups locally, nationally and internationally.

7.0 SUMMARY AND SIGNIFICANCE

Funding the Canadian Childhood Nephrotic Syndrome Project will address important unanswered questions in childhood nephrotic syndrome – what is the impact of variability in steroid treatments on patient outcomes (Objective 1) and who and what drives variability in care (Objective 2)? The integrated results of the study will allow us to develop best practice approaches for treatment of nephrotic syndrome and to develop an implementation plan to ensure uptake of our study results nationally and internationally. This study will provide key information to strategically prioritize future clinical trial questions (what to study, in which patients, when, and how to get buy-in from key stakeholders), and will build basic research infrastructure needed to conduct these trials to address critical knowledge gaps in the treatment of nephrotic syndrome. The novel national longitudinal web based patient data collection system developed as part of this study will also provide a platform to evaluate clinical care and outcomes on an ongoing basis in the future, and ultimately create a best practice approach to treatment of nephrotic syndrome.

REFERENCES

4. Arneil GC. Treatment of nephrosis with prednisolone. *Lancet*. Apr 14 1956;270(6920):409-411.
